9.4.5.4 Therapies used for accelerated elimination

Therapies used for accelerated elimination started between EOT and EOT + 15 days are summarized in the same way as for treatment concomitant therapies on the FAS. A listing of therapies used for accelerated elimination on the FAS is prepared.

9.4.6 Other subject characteristics

Other subject characteristics will be listed. This comprises the Chest X-Ray and Reproductive system findings.

9.5 Analysis of study treatment exposure and compliance

9.5.1 Exposure

Exposure to study drug [defined in Section 5.3.1] is summarized using descriptive statistics for continuous and categorical data using the SAF. In addition, this table displays the overall subject year exposure (sum over all subjects' exposure). Tables are presented by treatment group. All variables are also presented in subject data listings based on the SAF.

Subjects with at least one interruption, duration of interruptions as well as subjects with interruptions with reported reason will be summarized by treatment group on the SAF.

9.5.2 Compliance with study treatment

Compliance with study treatment variables [defined in Section 5.3.2] are summarized using descriptive statistics for continuous and categorical data using the SAF. Tables are presented by treatment group. All variables are also presented in subject data listings based on the FAS.

9.6 Analysis of the primary efficacy variable

9.6.1 Primary estimand

The primary estimand, the target for estimation in this study, is defined by the following components:

Population: Subjects with relapsing multiple sclerosis (RMS), as defined by the inclusion/exclusion criteria from the study.

Variable: ARR (number of confirmed relapses per subject-year) up to EOS, with EOS being at least 108 weeks after randomization [see Section 5.4.1].

Intercurrent events with corresponding strategies:

- **Treatment discontinuation:** Treatment Policy Strategy; including all confirmed relapses regardless of treatment discontinuation.

- **Start of alternative DMTs for MS:** Treatment Policy Strategy; including all confirmed relapses, regardless of start of alternative DMTs. Note: As per protocol alternative DMTs for MS are only allowed to be started after treatment discontinuation, therefore this intercurrent event is not expected to occur prior to or independent from treatment discontinuation.
- **Study discontinuation:** Hypothetical Strategy; effect if all subjects remained on study as planned per protocol. The assumptions for handling study discontinuation are detailed for the main analysis in Section 9.6.3 and for the sensitivity analyses on premature study withdrawal in Section 9.6.4.3.

Summary Measure: Rate ratio of ponesimod versus teriflunomide.

The primary analysis will be based on the Full Analysis set [see Section 7.1.2].

9.6.2 Hypothesis and statistical model

A generalized linear model with negative binomial distribution for the number of confirmed relapses will be assumed as described in Section 10.1.

Two-sided hypotheses are expressed in terms of the model parameters μ_{P20mg} and μ_{T14mg} . The primary null hypothesis is that the ARR (and consequently the model parameter μ) does not differ between ponesimod 20 mg and teriflunomide 14 mg. The alternative hypothesis is that the ARR differs between ponesimod 20 mg and teriflunomide 14 mg.

$$H_{0, ARR}: \mu_{P20mg} - \mu_{T14mg} = 0$$

versus

$$H_{1, ARR}: \mu_{P20mg} - \mu_{T14mg} \neq 0$$

The null hypothesis will be tested by a two-sided Wald test within the NB regression model, with a two-sided significance level of 0.01 for conclusive evidence and 0.05 for a positive study. Two-sided 99% and 95% Wald CIs and the associated p-value will be calculated for the relative reduction in mean ARR for ponesimod 20 mg compared to teriflunomide 14 mg.

9.6.3 Main analysis

The primary statistical analysis will be performed up to EOS on the FAS using an NB regression model for confirmed relapses, with treatment as a factor and the binary stratification variables (EDSS \leq 3.5 versus EDSS $>$ 3.5; DMT within last 2 years prior to randomization [Yes/No]) and the number of relapses in the year prior to study entry (categories \leq 1 [or missing, in order to avoid excluding subjects from the analysis] and \geq 2) included in the model. The model also includes an offset variable defined as the log of time on study (in years) from randomization up to EOS. The primary null hypothesis will be tested with a two-sided alpha level of 1% for conclusive evidence and 5% for a positive study.

Mean model-based estimates of the ARR (for confirmed relapses), by treatment arm, as well as 99% CIs and 95% CIs are presented. A rate ratio comparing ponesimod 20 mg with teriflunomide 14 mg will be derived from the model including 99% CIs, 95% CIs and the corresponding p-value. The dispersion parameter will also be displayed.

Descriptive summary statistics of the number of confirmed relapses as a continuous variable and the number of confirmed relapses in categories (0, 1, 2, 3, 4, ≥ 5), by treatment arm will be presented. The total cumulative number of confirmed relapses, as well as the total cumulative time on study (summed for all subjects) will also be displayed. From the total number of confirmed relapses and the total time on study the raw unadjusted ARR, by treatment arm, will be calculated and summarized.

The fit of the model will be assessed and other distributions such as the Poisson distribution will be considered in case of a lack of fit. The treatment-by-covariate interactions will also be assessed in separate models; if the interaction p-value is < 0.01 it will be investigated further to determine the nature of the interaction (quantitative or qualitative).

Handling of study discontinuation

For the main analysis it is assumed that follow-up time after study discontinuation is missing at random: a hypothetical scenario is considered assuming that subjects who discontinued the study would have similar efficacy as the subjects from the same treatment group who did not discontinue the study.

Sensitivity analyses on this assumption are described in Section [9.6.4](#).

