2 STUDY DESIGN AND FLOW

The study is a prospective, multicenter, randomized, double-blind, active-controlled, parallel-group, Phase 3, superiority study in adult subjects with relapsing forms of MS. 1133 subjects are randomized in two groups: ponesimod 20 mg or teriflunomide 14 mg, using a 1:1 ratio, stratified by use of multiple sclerosis (MS) disease-modifying treatment in the last two years prior to randomization (yes, no) and by baseline Expanded Disability Status Scale (EDSS) score ($EDSS \leq 3.5$, $EDSS > 3.5$).

The study is conducted at approximately 161 sites (randomized subjects) in 28 countries in North America, Eastern and Western Europe, and Pacific region.

[figure not shown]

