5.4 Efficacy variables

5.4.1 Primary efficacy variable(s): ARR up to EOS

The primary endpoint is the Annualized Relapse Rate (ARR) up to EOS, based on confirmed relapses according to the treating neurologist / principal investigator. ARR is defined as the number of confirmed relapses per subject-year.

For subjects completing the study as planned the EOS is scheduled to occur at least 108 weeks (± 7 days) after randomization.

More precisely, for subjects prematurely discontinuing treatment the EOS is scheduled to occur 108 weeks (± 7 days) after randomization. For subjects completing the 108-week treatment period the EOS is scheduled to occur prior to entry into the open-label extension (14–22 days after EOT, or 23–37 days after EOT in exceptional cases) or after the safety follow-up period for subjects not entering the open-label extension (30–37 days after EOT).

A confirmed relapse is defined as a record with ‘Relapse meeting the criteria for a confirmed relapse?’ answered ‘Yes’ on the ‘Relapse Summary’ eCRF. All confirmed relapses from randomization up to EOS will be included in the analysis.

For the statistical analysis of ARR, the following data will be used:

- Number of confirmed relapses from date of randomization up to EOS date;
- Length of observation expressed in years, defined as: $[\text{EOS date} - \text{date of randomization} + 1]$ in days, divided by 365.25.

The logarithm of the length of observation up to EOS will be used as an offset variable in the primary efficacy and sensitivity analyses.

Confirmed relapses ‘from date of randomization up to EOS date’ includes all confirmed relapses unless starting prior to randomization.

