The alpha level for the overall testing strategy across primary and secondary endpoints is set at 5%. Multiplicity adjustment as per the testing strategy outlined above will be performed. If the null hypothesis for the primary endpoint is rejected at two-sided alpha of 5% this leads to the example scenarios for alpha allocation for the secondary endpoints detailed as in Table 8.

Any further conducted tests will be considered exploratory.

Table 8 Example scenarios secondary endpoint alpha allocation

Scenario	Endpoint	Proportion of α	p-value for test	Statistically significant
1	Fatigue	1/3	$< 1/3 \alpha$	Yes
	CUALs	2/3	$< 2/3 \alpha$	Yes
	12-week CDA	1	$< \alpha$	Yes
	24-week CDA	1	$< \alpha$	Yes
2	Fatigue	1/3	$> 1/3 \alpha$	No
	CUALs	1/3	$< 1/3 \alpha$	Yes
	12-week CDA	2/3	$< 2/3 \alpha$	Yes
	24-week CDA	2/3	$< 2/3 \alpha$	Yes
3	Fatigue	1/3	$< 1/3 \alpha$	Yes
	CUALs	2/3	$> 2/3 \alpha$	No
	12-week CDA	1/3	$< 1/3 \alpha$	Yes
	24-week CDA	1/3	$< 1/3 \alpha$	Yes
4	Fatigue	1/3	$< 1/3 \alpha$	Yes
	CUALs	2/3	$< 2/3 \alpha$	Yes
	12-week CDA	1	$< \alpha$	No
	24-week CDA	0		
5	Fatigue	1/3	$> 1/3 \alpha$	No
	CUALs	1/3	$> 1/3 \alpha$	No
	12-week CDA	1/3	$< 1/3 \alpha$	Yes
	24-week CDA	1/3	$< 1/3 \alpha$	Yes
6	Fatigue	1/3	$> 1/3 \alpha$	No
	CUALs	1/3	$> 1/3 \alpha$	No
	12-week CDA	1/3	$> 1/3 \alpha$	No
	24-week CDA	0		

Scenarios for secondary endpoint alpha allocation are conditional on rejecting the primary null hypothesis.
 CDA = Confirmed disability accumulation; CUAL = Cumulative number of combined unique active lesions.

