9.7.1.2 Statistical Analysis

The main analysis will be based on the FAS. A mixed effect model repeated measures (MMRM) which includes baseline (FSIQ-RMS SWS_{c Base}) and the two stratification factors, i.e., prior use of DMT (Yes/No), baseline EDSS category (EDSS ≤ 3.5, EDSS > 3.5) as covariates, treatment (fixed effects), visit, treatment by visit interaction, and baseline (FSIQ-RMS SWS_{c Base}) by visit interaction is applied. An unstructured co-variance structure shared across treatment groups will be used to model within patient errors. The Kenwood Roger approximation will be used to estimate denominator degree of freedom and adjusted standard errors. This model assumes that missing data follow the

missing at random assumption. Subjects with at least one available score at a post-baseline visit and at the baseline visit are included in the analysis.

Treatment effects per visit are derived based on (difference in) least-square means with corresponding 95% CIs and p-values derived using the t-distribution. They will be presented in tabular and graphical form.

The main comparison for this secondary endpoint is conducted on the difference in least-square means at Week 108. The corresponding p-value is compared to the local significance level of $1/3 \alpha = 0.05/3$.

The SAS code for this model is as follows (considered “draft” until fully validated at analysis stage):

```
proc mixed data=;  
  class subject treatment visit DMT EDSS;  
  model Chg = Base DMT EDSS treatment visit treatment*visit Base*visit/ noint  
  ddfm=kr;  
  repeated visit / sub = subject type = un;  
  lsmeans Treatment*Visit / pdiff CL OM;  
run;
```

If the normality assumptions seems grossly violated the analysis will be conducted based on a rank ANCOVA of change from baseline to Week 108 using a stratified test [see Section 10.3.3].

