If the NB distribution is not considered to be appropriate (e.g. due to non-convergence), other distributions such as the Poisson and zero-inflated Poisson will be explored. For the Poisson distribution, a Poisson regression is conducted with model equation identical to the one for the negative binomial regression. The SAS code is as follows (considered "draft" until fully validated at analysis stage):

```
proc genmod data=ADREL;
  class Treat Strat Covar;
  model COUNTS = Treat Strat Covar / dist=poisson link=log
  offset = offset;
  lsmeans Treat / cl exp alpha = 0.01;
  estimate 'Ponesimod - Teriflunomide' || Treat 1 -1 / exp alpha = 0.01;
run;
```

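### Three alpha-controlled tests (ARR, CUAL, fatigue) can be exchanged for another model on undefined, data-dependent triggers; the fatigue switch is definite, and the Poisson option cannot cure overdispersion

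*SAP*

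**What the plan says.** **ARR (primary).** SAP 9.6.2 fixes the test: "The null hypothesis will be tested by a two-sided Wald test within the NB regression model, with a two-sided significance level of 0.01". Rejection at that level counts as conclusive; rejection at 0.05 alone makes the study positive. SAP 9.6.3 then provides for a check of model fit and says that "other distributions such as the Poisson distribution will be considered in case of a lack of fit".

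**CUAL.** SAP 9.7.2.2 specifies an NB model and repeats the same sentence.

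**Count data in general.** SAP 10.1, to which both hypothesis sections refer, applies when NB is judged inappropriate, with non-convergence given only as an example. In that case "other distributions such as the Poisson and zero-inflated Poisson will be explored". Its draft Poisson code has neither a scale option nor a robust variance.

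**Fatigue (FSIQ-RMS).** SAP 9.7.1.2 specifies an MMRM under missing at random, then adds: "If the normality assumptions seems grossly violated the analysis will be conducted based on a rank ANCOVA of change from baseline to Week 108". The stratified form of that procedure is set out in 10.3.3.

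**Multiplicity.** SAP 9.1.1 sets the total level: "The alpha level for the overall testing strategy across primary and secondary endpoints is set at 5" per cent. After a significant primary result, fatigue is tested at one third of alpha. CUAL gets one third or two thirds, depending on fatigue (Table 8).

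**The concern.** A test that carries alpha should be fixed before the data can influence it. Here the triggers are lack of fit, a judgement of inappropriateness, and an impression of gross non-normality. None has a criterion, and the SAP does not say that the judgement is made blind. Two analysts following this SAP could report different confirmatory p-values.

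The replacements raise further problems:

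- **Poisson** is a restricted form of NB. It cannot answer lack of fit caused by overdispersion; it only drops the term that allows for it.
- **Rank ANCOVA** changes what is tested. SAP 9.7.1.1 states the hypothesis as a difference in Week 108 means. SAP 10.3.3 tests the location of residual ranks and does not say how a missing Week 108 score is handled, whereas the MMRM uses every subject with a baseline and at least one post-baseline score.

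Fatigue comes first in the fallback sequence, so its result also sets the level for CUAL and can affect the level for 12-week CDA.

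**Working it through.** **Plan's own figure.** Three shares of 0.05/3 sum to 0.05, so the stated overall level is reproduced. The SAP version at hand has no sample-size or power figure to check.

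**Inputs from the SAP**
- Size and allocation: "1133 subjects are randomized in two groups", "using a 1:1 ratio" (section 2); 567 and 566 were used in the simulation.
- Follow-up: "For subjects completing the study as planned the EOS is scheduled to occur at least 108 weeks" (5.4.1). 108 × 7 / 365.25 = 2.07 years, with no dropout assumed.
- Levels: 5% and 1% for ARR; 0.05/3 = 1.67% or 2 × 0.05/3 = 3.33% for CUAL.

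**Assumed inputs (not in the SAP)**
- ARR: mean 0.4–0.7 confirmed relapses per subject, k 0.5–2.
- CUAL: mean 3–6 lesions per subject, k 1–2.

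**Formula.** For mean count μ and n subjects per arm, the model-based variance of the log rate ratio is the sum over arms of 1/(nμ) under Poisson and of (1 + kμ)/(nμ) under NB. Hence SE(NB)/SE(Poisson) = √(1 + kμ), and an unscaled Poisson Wald test at nominal α on NB data has true size 2·[1 − Φ(z/√(1 + kμ))], where z is the two-sided critical value for α.

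**Results**

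| Endpoint | μ, k | 1 + kμ | Nominal level | True size |
|---|---|---|---|---|
| ARR | 0.4, 0.5 | 1.2 | 5% / 1% | 7.4% / 1.9% |
| ARR | 0.6, 1 | 1.6 | 5% / 1% | 12.1% / 4.2% |
| ARR | 0.7, 2 | 2.4 | 5% / 1% | 20.6% / 9.6% |
| CUAL | 3, 1 | 4 | 1.67% / 3.33% | 23.1% / 28.7% |
| CUAL | 6, 2 | 13 | 1.67% / 3.33% | 50.7% / 55.5% |

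For example, ARR with μ = 0.6 and k = 1: 1.960/√1.6 = 1.549, giving 12.1%. CUAL with μ = 3 and k = 1: 2.394/√4 = 1.197, giving 23.1%.

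**Simulation check** (4000 trials per setting, no covariates, nominal 5%)

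| Setting | NB size | Unscaled Poisson size |
|---|---|---|
| 0.3 per year, k = 0 | 5.4% | 5.7% |
| 0.3 per year, k = 0.5 | 4.8% | 8.7% |
| 0.3 per year, k = 1 | 5.5% | 13.2% |
| 2 per year, k = 1 | 4.3% | 37.3% |
| 2 per year, k = 2 | 5.2% | 53.4% |
| 0.3 per year, variance/mean about 0.7 | 1.5% | 1.5% |

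The 2-per-year rows show the mechanism at CUAL-like rates; CUAL itself is never tested at 5%. The NB standard error was never below the Poisson one (smallest ratio 1.000). At k = 0 the two tests nearly agree. With underdispersed counts the estimated k was zero in every trial, and both tests were conservative.

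**Fatigue.** No arithmetic applies; the comparison is of text. SAP 9.7.1.1 and 9.7.1.2 give a Week 108 mean difference under missing at random. SAP 10.3.3 gives a rank test with no mean difference and no missing-data rule. The delta analysis in 9.7.1.3.1 follows the main analysis and pools a treatment difference, which a rank test would not supply.

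**The case against.** **Nothing is said to be replaced for ARR or CUAL.** The NB Wald test is fixed in 9.6.2 and 9.7.2.1, alternatives are only considered or explored, and 9.1.1 calls further tests exploratory. This largely stands: the text does not state that the confirmatory p-value would come from another model. But 9.1.1 does not address this case, and assessing the fit of the primary model with substitutes in mind invites that reading.

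**Poisson is not always anti-conservative.** This stands. A reader might infer that the switch can only make standard errors too small. That is true only relative to NB. Poisson is right at k = 0 and too cautious under underdispersion, and non-convergence, the one concrete trigger, can arise near k = 0.

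**The inflation figures are extreme cases.** They assume that unscaled Poisson is adopted for overdispersed data, where a fit check should show it doing worse than NB, and they rest on code marked as draft. Both are fair. The figures also do not cover zero-inflated Poisson; there the objection is only that the choice is undefined.

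**The rank ANCOVA is prespecified.** Its steps and code are given; the trigger and the missing-data handling are not. A reader might infer a Week 108 complete-case analysis. The SAP does not say so, and LOCF scores are derived elsewhere, so unspecified is the accurate word. No type I error inflation has been shown for this switch.

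**The choice may be made blind.** The SAP does not say when fit or normality is judged, so a choice after unblinding cannot be asserted; it is simply not excluded.

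**Conclusion.** The point holds. Three alpha-controlled tests have exits with no objective trigger and no requirement to decide blind. The fatigue exit is definite and changes both the hypothesis and the missing-data basis. The ARR and CUAL exits are a permitted reading, not a stated plan.

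If that reading were followed with the unscaled Poisson code and counts were overdispersed, the size of the test would be about 7–21% at nominal 5% for ARR (about 2–10% at nominal 1%). For CUAL it would be about 23–51% at nominal 1.67% and 29–56% at nominal 3.33%. These ranges rest entirely on the assumed means and k. At k = 0 there is no harm. With NB kept, the simulated size stayed between 4.3% and 5.5% in every setting with k of zero or more.

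**What to change.** - **9.6.3, 9.7.2.2 and 10.1:** state that the NB Wald test is the confirmatory test whatever the fit diagnostics show, and that other distributions, including zero-inflated Poisson, are sensitivity analyses. Section 10.1 must be edited too, or its open-ended wording survives.
- **Non-convergence only:** define it, and then use Poisson regression with subject-level robust (sandwich) variance and the same covariates and offset. Amend the draft code in 10.1 to match.
- **9.7.1.2:** state that the MMRM is always the confirmatory test. Make the rank ANCOVA a sensitivity analysis and state how it handles missing Week 108 scores.

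The cost is SAP wording and a small code change, with a possible small loss of power for fatigue if the score change is very skewed.

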9.6.4 Sensitivity analyses to main analysis

9.6.4.1 ARR based on confirmed relapses up to EOS on the FAS - unadjusted analysis

Same analysis as for the main analysis, but with treatment as the only factor in the model, i.e., not adjusting for covariates including stratification variables. This analysis is conducted to assess the effect of adjusting for covariates in the primary analysis.

9.6.4.2 ARR based on confirmed relapses up to EOS including derived stratification variable

Same analysis as for the main analysis, but instead of adjusting for the stratification variables from the IRT adjust for eCRF-derived stratification variables.

This analysis was requested by the FDA for the SPA review of study AC-058B302 and is performed to ensure that the results are consistent with the primary analysis, which are adjusted for the IRT stratification variables and – after eCRF data cleaning – might not match.

9.6.4.3 *ARR imputation analysis for subjects withdrawing from the study prematurely (imputation from EOS to theoretical Week 108)*

To assess the impact of subjects withdrawing from the study prior to Week 108, sensitivity analyses will be performed. These include the imputation of confirmed relapses using various assumptions for the period with missing data.

The proportion of missing data, i.e., missing observation time, will be calculated as

$$1 - \frac{\text{Cumulative time between randomization and EOS (or theoretical Week 108, if earlier)}}{\text{Cumulative time between randomization and theoretical Week 108}}$$

and will be summarized descriptively. Time up to EOS (i.e., time in study) will be presented based on an inverse cumulative distribution function [see Section 9.3.1].

Multiple imputation (MI) methods for count data are applied, following the approach from Keene 2014; see Section 10.1.1 for details.

Number of relapses between EOS and theoretical Week 108 will be imputed for subjects who have prematurely discontinued from the study.

Several approaches will be used for the imputation of events:

- **Missing at random (MAR) MI approach:** Under this approach, the rate after withdrawal for each treatment arm is assumed to be the rate in the respective arm before withdrawal.
- **Reference-based MI approaches:** The rate in the reference (teriflunomide 14 mg) arm is used for imputation in both the ponesimod 20 mg and teriflunomide 14 mg arms. While the post-withdrawal events in the teriflunomide 14 mg arm are imputed under the MAR assumption for that arm, two different approaches are applied for the imputation of the post-withdrawal events in the ponesimod arm:
 - a. **Copy reference MI approach:** Impute based on the reference arm; For a subject in the ponesimod arm, if the event rate prior to withdrawal is *better than would be expected on the reference arm*, under this approach, their imputed event rate after withdrawal will also be *better than the expected event rate on the reference arm*. The copy reference imputation is expected to be less favorable for ponesimod 20 mg as compared to MAR approach as it is relative to the rate in the reference arm, but not as extreme as the jump to reference approach described below.
 - b. **Jump to reference MI approach:** Impute based on the reference arm; For a subject in the ponesimod arm, if the event rate prior to withdrawal is *worse than would be expected on the ponesimod arm*, under this approach, their imputed event rate after withdrawal will be *worse than the expected event rate on the reference arm*. This approach assumes that withdrawn subjects on the ponesimod

20 mg treatment will quickly lose any positive effect of their treatment (relative to the reference arm) when it is stopped.

The resulting rate ratio and corresponding 99% and 95% CIs will be reported and presented in tables and graphically.

A delta-adjustment MI method [Keene 2014] will also be applied to further assess deviations from the MAR assumption:

- **Delta adjustment MI approach:** Starting with the MAR assumption for both treatment arms, a 2-way delta adjustment is applied.

Ponesimod 20 mg arm: The rate after withdrawal is multiplied by δ_P , ranging from 1 (MAR, i.e. same rate as prior to withdrawal) to 3.1 (~Tripling of relapse rate) in steps of 0.3.

Teriflunomide 14 mg arm: The rate after withdrawal is multiplied by δ_T , ranging from 0.1 (relapse rate reduced by 90%) over 1 (MAR, i.e. same rate as prior to withdrawal) to 3.1 (~tripling of relapse rate) in steps of 0.3.

For each imputed dataset the same negative binomial regression model as for the primary analysis will be fit and results will be combined using Rubin's rule [see Section 10.1.1].

The resulting rate ratios and corresponding 99% CIs and p-values will be reported and presented in tables and graphically.

